2.5 Rationale for choice of comparators drugs

Not applicable

3 Objectives and endpoints

Objectives and related endpoints are described in [Table 3-1](#) below.

Table 3-1 Objectives and related endpoints

Objective	Endpoint	Analysis
Primary		Refer to Section 10.4
To evaluate patient preference between deferasirox FCT and deferasirox DT	Proportion of patient claimed preference of deferasirox FCT over deferasirox DT as measured by preference questionnaire at Week 48	
Secondary		Refer to Section 10.5.1
To evaluate patient preference of deferasirox FCT or deferasirox DT or previous iron chelation	Proportion of patient claimed preference of deferasirox FCT, deferasirox DT, and previous iron chelation as measured by preference questionnaire at Week 28	
To evaluate patient preference of deferasirox DT or previous iron chelation	Proportion of patient claimed preference of deferasirox DT, over previous iron chelation as measured by preference questionnaire at Week 4 and Week 24	
To evaluate the reason behind preference for deferasirox FCT or deferasirox DT	Proportion of preference reasons for deferasirox FCT over deferasirox DT as measured by preference questionnaire at Week 28 and Week 48	
To evaluate the effect of deferasirox FCT compared with deferasirox DT on patient compliance using pill count	Relative consumed pill count during deferasirox FCT (Week 25 to 48) compared with deferasirox DT (Baseline day 1 to Week 24)	
To evaluate the effect of deferasirox FCT compared with deferasirox DT or previous iron chelation on patient palatability using PRO	Absolute and relative change in domain scores of palatability questionnaire over time during deferasirox FCT (Week 28 to 48) compared with deferasirox DT (Week 4 to 24) or previous iron chelation (Screening)	
To evaluate the effect of deferasirox FCT compared with deferasirox DT or previous iron chelation on patient satisfaction using PRO	Absolute and relative change in domain scores of SICT questionnaire over time during deferasirox FCT (Week 28 to 48) compared with deferasirox DT (Week 4 to 24) or previous iron chelation (Screening)	
To evaluate the effect of deferasirox FCT compared with deferasirox DT or previous iron chelation on patient GI symptom using PRO	Absolute and relative change in domain scores of SICT questionnaire over time during deferasirox FCT (Week 28 to 48) compared with deferasirox DT (Week 4 to 24) or previous iron chelation (Screening)	

Objective	Endpoint	Analysis

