5.2 Inclusion criteria

Patients eligible for inclusion in this study have to meet **all** of the following criteria:

1. Prior to any screening procedures being performed, written informed consent/assent must be provided. For pediatric patients, consent will be obtained from the parent(s) or the patient's legal representative. Investigators will also obtain assent of patients according to local, regional or national guidelines.
2. Male and female patients aged ≥ 2 years
3. Deferasirox naïve patient or a chelation naïve patient or a patient treated by other chelators for at least 6 months continuously, such as:
 - a. Deferiprone (DFP)
 - b. Deferoxamine (DFO)
 - c. Combination (DFO + DFP)
4. Subject is willing to discontinue current iron chelation therapy at least 5 days prior to the Study day 1 and for the duration of the study
5. Patients with transfusion-dependent thalassemia (independent of underlying condition) with transfusional iron overload as shown by:
 - a serum ferritin level of > 1000 ng/ml at screening and if available, LIC > 3 mg Fe/g dw within 6 months prior to screening
6. Patients with non-transfusion-dependent thalassemia with iron overload as shown by:
 - a serum ferritin level of ≥ 800 ng/ml at screening and if available, LIC ≥ 5 mg Fe/g dw within 6 months prior to screening

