⁴ The study will last until one of the patient withdrawal criteria is met ([Section 7.1.3.1](#)). At that time, the patient needs to complete the Study Evaluation Completion (SEC / 777) visit, and then FUP visit 30 days after last dose of study drug.

⁵ Last dose of deferasirox DT will be dispensed on Week 24, and taken by the patient until Week 24 day 7. At the Week 24 visit, the site will also dispense deferasirox FCT. The patient will take the first dose on Week 25 day 1.

⁶ Week 48 Visit (visit number 15) is a combined visit as it is the last visit of the Core Phase and the Baseline visit for the extension phase

⁷ If the patient switches treatment, the investigator must provide the preference questionnaire to the patient in the immediate next visit. Please refer to [Appendix 14.3](#) for further information.

⁸ "PROs" include observer reports for patients 2-9 years old

⁹ Palatability, satisfaction and GI symptoms questionnaires will be provided to the patient on Screening (visit number 1), during the 5 days of wash-out period from previous iron chelators therapies

¹⁰ Completion of PRO questionnaires at screening visit for ICT naïve patient or patients who did not take any ICT treatment within the 6 months prior to screening is not required

[figure not shown]
¹¹ Completion of palatability questionnaires at screening visit for patients who received Deferoxamine as prior chelation therapy is not required

¹² All Baseline assessments indicated in [Table 7-1](#) and [Table 7-2](#) must be completed prior to initiating Deferasirox DT treatment.

¹³ The investigators will have to re-assess, every 6 months, the childbearing potential of female patients aged 13 and older who are pre-menarche at the time of enrolling in the study. Once patient is able to bear children, they will need to undergo a urine pregnancy test in the next consecutive visit and then follow the VES for the urine and serum pregnancy tests.

Table 7-2 Visit Evaluation Schedule - Extension Phase

	Category	Protocol Section 7.2	Baseline EXT	EXTENSION PHASE treatment ⁴											Study Evaluation Completion ²	Safety Follow up
Visit Number			15 ⁵	16	17	18	19	20	21	22	23	24	25	26	777	501
Study Week			W48 (M12)	W52 (M13)	W56 (M14)	W60 (M15)	W64 (M16)	W68 (M17)	W72 (M18)	W76 (M19)	W80 (M20)	W84 (M21)	W88 (M22)	W92 (M23)	W96 (M24)	30 days after last dose of study drug received
Informed consent	(D)	7.1.1														
Inclusion/exclusion criteria	(D)	7.1.1.1														

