7.3.4 GI Symptoms – patients greater or equal to 10 years old

The GI symptom questionnaire consists of 6 items, 5 of which are scored using a 0 – 10 rating scale with item appropriate end anchors to rate the symptom, for example Pain in your belly 0 = no pain and 10 = worst pain, with the numbers 1-9 labeled in between. The sixth item assesses bowel movement frequency during the past 24 hours, using 7 response options 0 = 0 (none), 1 = 1, 2 = 2, 3 = 3, 4 = 4, 5 = 5 – 10 and 6 = 11 or more.

A GI summary score will be created using the 10 point response scale items (5 items), Item 6 will be excluded from the calculation of the GI symptom summary score and used in the analysis as a standalone item. Overall, higher scores on the GI symptom diary items and the summary score will indicate worse symptoms.

Weekly GI diary symptoms summary scores as well as item 6 (bowel movement) will be summarized using descriptive statistics at Screening, week 4, week 24, week 28 and week 48.

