### **Baseline assessment:**

Baseline assessment in general will be defined as the last assessment prior to the start of the study treatment which is the assessment taken at Day 1 of study. A baseline value refers to the last measurement made prior to administration of first dose of study treatment.

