### **Palatability using PRO/ ObsRO questionnaire**

The palatability questionnaire consists of 4 items. Two items measure the taste and aftertaste of the medication and are scored on a 5 point response scale. The remaining palatability items refer to whether the medication was taken (i.e. swallowed or vomited) and how the patient perceived the amount of medication to be taken.

For the palatability questionnaire the overall score will be constructed using a scoring matrix from the score of items. Standard descriptive analyses including absolute and relative changes will be performed for both formulations (DT/FCT) for the overall score at Week 4, Week 24, Week 28 and Week 48 and overall score at Screening for iron chelators. The baseline data for treatment period 1 and 2 will be Week 4 and Week 24 data respectively, only one assessment is observed at Screening period. The summary will be provided separately for PRO and ObsRO patient groups.

The standard descriptive analyses include: n, mean, standard deviation, minimum, median and maximum. The 95% CI for the absolute and relative (or difference) change from baseline of the overall score will also be presented for the treatments.

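### Previous chelation is a named comparator for palatability, satisfaction and GI symptoms, but no paired change from it is defined, and the DT and FCT change scores measure different things

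*Protocol*

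**What the plan says.** **Comparator.** For palatability, satisfaction and GI symptoms, Protocol Table 3-1 defines the endpoint as absolute and relative change during FCT "compared with deferasirox DT (Week 4 to 24) or previous iron chelation (Screening"). SAP Table 1.2.1 repeats this. In both tables the GI row names the SICT questionnaire instead of the GI questionnaire.

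**Baselines.** For palatability and mSICT, SAP 2.11 states: "The baseline data for treatment period 1 and 2 will be Week 4 and Week 24 data respectively". Protocol 10.5.6 has the same rule. The Screening score is summarised as a level for the previous chelators. The SAP's general rule (2.1.1) is: "A baseline value refers to the last measurement made prior to administration of first dose of study treatment".

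**GI analysis.** Protocol 10.5.6 says that GI symptoms are handled by analogy with the other questionnaires. SAP 2.11 promises only a summary and a listing, with no baseline or change score. SAP 4 declares no departure from the protocol's analyses.

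**Who has a Screening score.** Protocol Table 7-1, footnotes 10 and 11: none is required from chelation-naïve patients or those without chelation in the previous 6 months, and no palatability form is required after deferoxamine.

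**When it is completed.** Footnote 9: "Palatability, satisfaction and GI symptoms questionnaires will be provided to the patient on Screening (visit number 1), during the 5 days of wash-out period". Inclusion criterion 4: "Subject is willing to discontinue current iron chelation therapy at least 5 days prior to the Study day 1".

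**GI recall.** For patients aged 10 or over, Protocol 7.3.4 says: "The sixth item assesses bowel movement frequency during the past 24 hours". It adds: "Item 6 will be excluded from the calculation of the GI symptom summary score". No recall window is given for the five scored items. The nearest hint is the phrase "Weekly GI diary symptoms summary scores". The observer GI items listed in SAP 2.11 look back 2 weeks, whereas Protocol 7.3.5 says that the observer items match the patient items.

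**The concern.** Three secondary objectives ask how deferasirox compares with the chelator the patient took before. An answer within patients needs a paired difference from Screening, and none is planned. The two change scores that are planned will appear with confidence intervals by treatment, which invites the reader to compare them. The DT score leaves out the effect of starting DT, because its reference is taken four weeks into DT. The FCT score contains the effect of moving to FCT.

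For GI there is a second problem. Taste and satisfaction can be recalled after stopping a drug. A symptom question tied to a recent calendar window describes whatever the patient was taking in that window. If the form is completed during the wash-out, part of the window may be free of the previous chelator, while the DT and FCT scores are taken on treatment.

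**Working it through.** The plan gives no figure to reproduce here. The check is of what each planned quantity contains, followed by one short calculation.

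**1. Content of the change scores.** Write P for the Screening score, D4 and D24 for the DT scores at Weeks 4 and 24, and F for the FCT score at Week 28 or 48. Then

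F − P = (D4 − P) + (D24 − D4) + (F − D24).

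The plan's Period 1 change is the second term and its Period 2 change is the third. The first term, the step from previous chelation to DT, appears in neither.

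**2. Invented illustration on the 0–11 palatability score.** Take P = 10, D4 = 4, D24 = 4, F = 10.

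| Quantity | DT | FCT |
|---|---|---|
| Change as planned | 4 − 4 = 0 | 10 − 4 = +6 |
| Change from Screening | 4 − 10 = −6 | 10 − 10 = 0 |

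The planned scores suggest no effect of DT and a gain with FCT. Measured against the previous chelator, DT is worse and FCT is equal.

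**3. Can the reported levels fill the gap?** Only in part. The Screening mean comes from pre-treated patients, and for palatability excludes those for whom no form was required after deferoxamine. The means at Weeks 4 to 48 come from all patients in the FAS with data. A difference of these means mixes the within-patient change with a change in who is counted. Presentation by chelation status (SAP 2.1) removes the naïve patients but does not separate out those previously on deferoxamine. A confidence interval for the paired difference cannot be derived from two separate summaries, because the within-patient correlation is missing.

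**4. Share of the GI recall window off the previous chelator.** With k full days since the last dose and a window of R days, the share is min(k, R)/R. Inputs: k = 0 to 5 (5-day wash-out, footnote 9); R = 1 (item 6, Protocol 7.3.4); R = 14 (observer items, SAP 2.11); R = 7 is an assumption from the word weekly in Protocol 7.3.4.

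| k | R = 1 (item 6, not scored) | R = 7 (assumed, five scored items) | R = 14 (observer items) |
|---|---|---|---|
| 0 | 0% | 0% | 0% |
| 1 | 100% | 1/7 = 14% | 1/14 = 7% |
| 3 | 100% | 3/7 = 43% | 3/14 = 21% |
| 5 | 100% | 5/7 = 71% | 5/14 = 36% |

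These are shares of the window, not amounts of bias. The completion day is itself loose: Screening may be up to 28 days before Day 1, and criterion 4 sets 5 days as a minimum, so k can differ between patients.

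**The case against.** **The Week 4 baseline is deliberate and has a use.** The SAP's baseline definition applies in general, and a specific rule for questionnaires may depart from it. The endpoint is worded as change over time within Weeks 4 to 24, which Week 24 minus Week 4 matches. Week 4 is also the first questionnaire scheduled for every patient; dropping it would leave naïve patients, and deferoxamine patients for palatability, with no Period 1 change. This stands. A reader might infer that the Week 4 baseline contradicts the SAP and should go, and the documents do not support that. They support only that it cannot serve the comparison with previous chelation, or be set beside the FCT change as a treatment contrast.

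**The score levels are reported.** A sequence such as 10, 4, 4, 10 would be visible in the visit summaries. This is true, but it does not give a paired estimate in a common set of patients.

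**The GI comparison is not shown to be biased.** A reader might infer that the GI score for previous chelation is an off-drug value that makes both deferasirox formulations look worse. The documents do not support this. The only 24-hour item is left out of the summary score, and the five scored items have no stated window. For the observer items, at least 9 of 14 days precede a 5-day wash-out. Protocol 7.3 exempts naïve patients because they have no chelator experience to report, which suggests that the forms ask about experience on the chelator. The direction would also require that the previous chelator caused GI symptoms which resolve within days, and neither document gives such data. This objection stands.

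**Limited weight and late timing.** SAP 2.7.2 plans no formal testing of secondary endpoints. Amendment 1 records 132 patients enrolled of about 145, and the current SAP follows the interim database lock. Both points stand and shape the fix.

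**Conclusion.** The point holds for the change scores, and this part rests on the documents alone. Three secondary objectives name a comparator from which no paired change is formed. The DT and FCT changes differ in kind, and for GI the SAP defines no change at all although the protocol asks for an analysis analogous to the others.

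On wash-out timing only a limited statement holds: the GI value filed as previous chelation may include off-chelator days. The possible share runs up to 100% for the unscored 24-hour item and up to 36% for the observer items, both assuming completion within a 5-day wash-out. For the five scored items it is unknown (up to 71% if the window is 7 days). Size and direction of any bias cannot be established.

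The primary preference analysis is untouched. The point is worth correcting because otherwise the report cannot answer its stated objective on previous chelation.

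**What to change.** 1. In Protocol 10.5.6 and SAP 2.11 together, so that they do not diverge, add for pre-treated patients with a Screening score the paired difference from Screening at Weeks 4 and 24 (DT) and Weeks 28 and 48 (FCT), with 95% CI, for palatability, mSICT and GI. Report the number of pairs each time.
2. Keep Week 24 as the reference for FCT minus DT. Keep Week 24 minus Week 4 for all patients, labelled as a within-DT change over time, and do not present it beside the FCT change as a treatment comparison.
3. Flag each GI Screening form as on or off chelator, using the prior-chelation end date from which SAP 2.3.3 already derives time since last chelation. Repeat the GI comparison in forms completed within one day of the last dose. This assumes that the form's completion date, or the Visit 1 date in its place, is in the database.
4. State the recall window of every GI item, reconcile the observer GI items between Protocol 7.3.5 and SAP 2.11, and correct the questionnaire named in the GI endpoint row.
5. For any patients still to be screened, have the GI form completed at Visit 1 before the wash-out starts. The wash-out itself does not change.

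**Cost:** a few sentences in each document and some extra tables, with no new visit or questionnaire. The comparison with previous chelation will rest on fewer patients, and the GI repeat on fewer still. The added analyses must be declared as introduced after the interim database lock.

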4.4 Definition of end of study

All patients must remain within the study until Week 48 (last visit on Core Phase) unless one of the criteria defined in [Section 7.1.3](#) (definition of premature patient withdrawal) is met, in which case, the patient must discontinue from the study and complete the Study Evaluation Completion Visit (SEC - visit number 777) within 7 days of discontinuing treatment. A patient will be considered as having “completed the study” if all the visits have been performed from Screening (visit number 1) to Week 48 (visit number 15).

The end of study is defined as the earliest occurrence of one of the following:

- The patient has reached Week 96 at Extension phase.
- Deferasirox FCT is locally reimbursed for this indication (only applicable in Extension phase)
- Another clinical study or post-trial access program becomes available that can continue to provide deferasirox FCT in this patient population and all patients ongoing are eligible to be transferred to that clinical study

The investigator will be responsible for informing IRBs and/or EC.

Patients will perform a safety follow up visit 30 days after the last dose of study drug.

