5.3 Exclusion criteria

Patients eligible for this study must not meet **any** of the following criteria:

1. Creatinine clearance below the contraindication limit in the locally approved prescribing information.
2. Serum creatinine level > 1.5 x ULN (upper limit of normal)
3. AST (SGOT) /ALT (SGPT) > 5 x ULN, unless LIC confirmed as >10 mg Fe/dw within 6 months prior to screening visit.
4. Significant proteinuria as indicated by a urinary protein/creatinine ratio > 0.5 mg/mg in a non-first void urine sample.
5. Patients with significant impaired gastrointestinal (GI) function or GI disease that may significantly alter the absorption of oral deferasirox (e.g. ulcerative diseases, uncontrolled nausea, vomiting, diarrhea, malabsorption syndrome, or small bowel resection).
6. Clinical or laboratory evidence of active Hepatitis B or Hepatitis C (HBsAg in the absence of HBsAb OR HCV Ab positive with HCV RNA positive).

7. Patients with psychiatric or addictive disorders which prevent them from giving their informed consent or undergoing any of the treatment options or patients unwilling or unable to comply with the protocol.
8. Patients with a known history of HIV seropositivity (Elisa or Western blot).
9. History of malignancy of any organ system, treated or untreated, within the past 5 years whether or not there is evidence of local recurrence or metastases, with the exception of localized basal cell carcinoma of the skin.
10. Patients participating in another clinical trial or receiving an investigational drug. Patients who have recently completed treatment with an investigational product must have ceased this treatment for at least five times the half-life of the investigational product.
11. History of hypersensitivity to any of the study drug or excipients.
12. Significant medical condition interfering with the ability to partake in this study (e.g. systemic uncontrolled hypertension, unstable cardiac disease not controlled by standard medical therapy, systemic disease (cardiovascular, renal, hepatic, etc.).
13. Women of child-bearing potential, defined as all women physiologically capable of becoming pregnant, **unless** they are using effective methods of contraception during dosing of study treatment. Effective contraception methods include:

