History of disease	(D)	7.1.1.3														
Demography	(D)	7.1.1.3														
Relevant medical history/current medical conditions	(D)	7.1.1.3														
Prior chelation therapy ¹	(D)	7.1.1.3														
Transfusion/RBC History	(D)	7.1.1.3														
Transfusions received	(D)	7.1.2	X	X	X	X	X	X	X	X	X	X	X	X	X	
Physical exam	(S)	7.2.2.1	X	X	X	X	X	X	X	X	X	X	X	X	X	
Weight	(D)	7.2.2.3	X	X	X	X	X	X	X	X	X	X	X	X	X	
Height	(D)	7.2.2.3	X													

[figure not shown]
Visit Number	Category	Protocol Section 7.2	Baseline EXT	EXTENSION PHASE treatment ⁴											Study Evaluation Completion ²	Safety Follow up
				15 ⁵	16	17	18	19	20	21	22	23	24	25		
Study Week			W48 (M12)	W52 (M13)	W56 (M14)	W60 (M15)	W64 (M16)	W68 (M17)	W72 (M18)	W76 (M19)	W80 (M20)	W84 (M21)	W88 (M22)	W92 (M23)	W96 (M24)	30 days after last dose of study drug received
Vital signs	(D)	7.2.2.2	X	X	X	X	X	X	X	X	X	X	X	X	X	
Ocular exam	(D)	7.2.2.5	X													
Audiometry	(D)	7.2.2.5	X													
ECG	(D)	7.2.2.7.1	X													
Chest X-ray (if clinically indicated)	(D)	7.2.2.4	X													
Prior and Concomitant medications	(D)		X	X	X	X	X	X	X	X	X	X	X	X	X	
Adverse events	(D)	7.2.2	X	X	X	X	X	X	X	X	X	X	X	X	X	X
Laboratory assessments- Blood																
Hematology	(D)	7.2.2.6.1	X	X	X	X	X	X	X	X	X	X	X	X	X	
Biochemistry	(D)	7.2.2.6.2	X	X	X	X	X	X	X	X	X	X	X	X	X	
Serum ferritin	(D)	7.2.1	X	X	X	X	X	X	X	X	X	X	X	X	X	
Serum creatinine	(D)	7.2.2.6.2	X	X	X	X	X	X	X	X	X	X	X	X	X	
Creatinine clearance	(D)	7.2.2.6.2	X	X	X	X	X	X	X	X	X	X	X	X	X	

	Category	Protocol Section 7.2	Baseline EXT	EXTENSION PHASE treatment ⁴											Study Evaluation Completion ²	Safety Follow up
Visit Number			15 ⁵	16	17	18	19	20	21	22	23	24	25	26	777	501
Study Week			W48 (M12)	W52 (M13)	W56 (M14)	W60 (M15)	W64 (M16)	W68 (M17)	W72 (M18)	W76 (M19)	W80 (M20)	W84 (M21)	W88 (M22)	W92 (M23)	W96 (M24)	30 days after last dose of study drug received
Serum/ urine pregnancy test ^{3, 6}	(D)	7.2.2.6.4	X													
Laboratory assessments- Urine																
Urine dipstick	(D)	7.2.2.6.3	X	X	X	X	X	X	X	X	X	X	X	X	X	
Microscopic urine	(D)	7.2.2.6.3	X	X	X	X	X	X	X	X	X	X	X	X	X	
Proteinuria (urine protein/ creatinine ratio)	(D)	7.2.2.6.3	X	X	X	X	X	X	X	X	X	X	X	X	X	
Other assessments																
Deferasirox FCT drug administration	(D)		X	X	X	X	X	X	X	X	X	X	X	X	-	
Dispensed/ returned FCT count	(D)	7.2.4	X	X	X	X	X	X	X	X	X	X	X	X	X	

¹ Includes 5-day washout period from previous iron chelation therapy.

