² Study Evaluation Completion visit will be undertaken for all patients completing the study or discontinuing earlier for any reason. Please refer to [Section 7.1](#) for further information.

³ A serum pregnancy test can also be carried out at any time if deemed necessary by the investigator.

⁴ The study will last until one of the EOS criteria is met ([Section 4.4](#)). At that time, the patient needs to complete the Study Evaluation Completion (SEC) visit, and then FUP visit 30 days after last dose of study drug.

⁵ Week 48 Visit (visit number 15) is a combined visit as it's being identified as the last visit of the Core Phase and the Baseline visit for the extension phase (if none of the End Of Study criteria is met)

⁶ The investigators will have to re-assess, every 6 months, the childbearing potential of female patients aged 13 and older who are pre-menarche at the time of enrolling in the study. Once a patient is able to bear children, they will need to undergo a urine pregnancy test at the next consecutive visit and then follow the VES for the urine and serum pregnancy tests thereafter.

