7.1.2 Treatment period

The duration of core phase treatment is 48 weeks. Patient visits will occur every 2 weeks during the first month of treatment and then every 4 weeks thereafter until Visit 777 (SEC).

Having completed the screening period (including the 5-day wash out period for patients previously treated with deferiprone (DFO) or deferoxamine (DFP)), patients who are eligible will be enrolled to receive deferasirox DT during 24 weeks then switch to deferasirox FCT for 24 weeks. Daily dose is calculated by the physician based on the patient's actual body weight.

At the start of treatment, iron chelation naïve patients will receive deferasirox DT 10 mg/kg (NTDT patients) or 20 mg/kg (TDT patients) once daily then will transition to the equivalent FCT dose as outlined in the following table.

Table 7-3 Equivalent dose to be used: Deferasirox DT vs Deferasirox FCT

Equivalent dose to be used	
Deferasirox DT (mg/kg/day)	Deferasirox FCT (mg/kg/day)
5	3.5
10	7
15	10.5
20	14
25	17.5
30	21
35	24.5
40	28

All iron chelation pre-treated patients will follow the below guidance:

Patients who were taking deferoxamine (DFO), will need to take the deferasirox DT equivalent deferasirox. For deferiprone (DFP) the dose of deferasirox DT will be based on their serum ferritin. Please refer to [Table 6-2](#).

At the Week 48 visit, patients will roll over to the extension phase in the case that none of the End of Study criteria is met at that time. The patient will receive deferasirox FCT following the same dose regulations and adjustments as per the core phase.

The treatment period of the extension study is approximately 52 weeks (including treatment period (48 weeks), Study Evaluation Completion and 4 weeks Safety Follow-up visits)

For details on study design and dose adjustments, see [Section 4](#) and [Section 6.3](#).

For details of assessments, see [Table 7-1](#) and [Table 7-2](#).

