7.2.2.6.4 Pregnancy and assessments of fertility

All female patients capable of becoming pregnant will have a pregnancy test (serum β -HCG) at the screening visit and visit 15. An urine pregnancy test will be performed as described in [Table 7-1](#) and [Table 7-2](#). The results of the test must be available prior to initiating treatment with any study medication. Positive pregnancy tests will exclude a patient from participating in this trial.

Pregnancy must be recorded on a Clinical Trial Pregnancy Form and reported by the investigator to the local Novartis Clinical Safety & Epidemiology Department. Pregnancy follow-up must be recorded on the same form and must include an assessment of the possible relationship to the Novartis study drug of any pregnancy outcome. Any SAE experienced during pregnancy must be reported on the SAE Report Form.

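### The only explicit re-check of childbearing potential after Day 1 is limited to females aged 13 and older, so menarche before 13 prompts no scheduled re-check before that age

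*Protocol*

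**What the plan says.** Inclusion criterion 2 (Protocol 5.2) admits "Male and female patients aged ≥ 2 years". Treatment is 48 weeks in the core phase and can continue in the extension until "The patient has reached Week 96 at Extension phase" (4.4). Visits are two-weekly in the first month and four-weekly after that (7.1.2).

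Two safety rules depend on whether a patient can conceive, and neither names an age. Exclusion criterion 13 (5.3) requires effective contraception during dosing for "Women of child-bearing potential, defined as all women physiologically capable of becoming pregnant". Section 7.2.2.6.4 states that "All female patients capable of becoming pregnant will have a pregnancy test", with serum tests at screening and Visit 15 (Week 48); Table 7-1 adds a urine test on Day 1. Eligibility is checked at screening and verified again on Day 1 (7.1.1.3), so girls who are already post-menarche at entry are covered.

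For girls who are pre-menarche at entry, Table 7-1 footnote 13 and Table 7-2 footnote 6 tell investigators to "re-assess, every 6 months, the childbearing potential of female patients aged 13 and older who are pre-menarche" when they enrol. The next sentence of the footnote has no age limit: once a patient can bear children, "they will need to undergo a urine pregnancy test at the next consecutive visit" and the visit schedule's tests apply from then on. Neither the protocol nor the SAP contains any other instruction to re-assess childbearing potential after Day 1.

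**The concern.** The footnote exists because a girl can become fertile during the study. It is the step that moves her from outside the contraception and testing rules to inside them. Those rules are defined by physiology; the step that triggers them is defined by age, and the documents give no reason for choosing 13. A girl whose menarche comes earlier is in scope of the rules but out of scope of the check that would reveal it.

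What is at stake is when fertility is recognised. Contraception counselling and the triggered urine test begin only after someone has noticed. Section 11.3 tells women of childbearing potential that risks to a fetus are unknown, and section 7.1.3.1 lists pregnancy as a reason for withdrawal that a change of formulation cannot avoid.

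The wording is also unclear on whether 13 is the age at enrolment or at the time of the check, so sites could apply it differently.

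**Working it through.** There is no planned figure to reproduce. The check compares the rules and then does date arithmetic.

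**Scope of each rule**

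| Rule | Who is covered | Age limit |
|---|---|---|
| Inclusion 2 | all patients | from 2 years |
| Exclusion 13 (contraception) | any female able to conceive | none |
| 7.2.2.6.4 (serum test, screening and Week 48) | any female able to conceive | none |
| Footnotes 13 and 6, first sentence (six-monthly re-check) | pre-menarche at enrolment | 13 and older |
| Footnotes 13 and 6, second sentence (urine test once fertile) | any patient found to be fertile | none |

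Only the re-check carries the limit.

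**Reading A: age at enrolment.** A girl enrolled pre-menarche under 13 has no re-check under the footnote at any time, even after she turns 13.

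**Reading B: current age.** She has no re-check until she is 13. The baseline age below which she is still under 13 at week w is

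cut-off = 13 − 7w/365.25

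- Week 48: 13 − 336/365.25 = 13 − 0.92 = 12.08 years.
- Week 96: 13 − 672/365.25 = 13 − 1.84 = 11.16 years.

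If age is recorded at consent, up to 28 days earlier, each cut-off falls by up to 28/365.25 = 0.08 years, to 12.00 and 11.08 years.

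**Comparison.** A pre-menarchal girl aged 13 or older at entry has 3 re-checks over 672 days if six months is a calendar interval (672/182.625 = 3.68). She has 4 if it is counted in 24-week steps (672/168 = 4). A girl below about 11.16 years at baseline has 0 under either reading.

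**Illustration of the delay under Reading B.** The ages are assumed: 11.3 years at baseline, menarche at 12.5.

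- Menarche falls at (12.5 − 11.3) × 365.25/7 = Week 62.6, after the Week 48 serum test.
- If checks fall at Weeks 24, 48, 72 and 96, she is 12.68 years at Week 72 (too young) and 13.14 at Week 96. The first check comes 96 − 62.6 = 33.4 weeks after menarche.
- If the cycle starts when she turns 13, that is (13 − 11.3) × 365.25/7 = Week 88.7. The next visit is Week 92, and the delay is 92 − 62.6 = 29.4 weeks.
- With no age limit and the Week 24/48/72/96 pattern, she is checked at Week 72, a delay of 72 − 62.6 = 9.4 weeks.

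The footnote fixes no anchor, so the delay of 29 to 33 weeks shows the mechanism and is not an estimate for the trial.

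**The case against.** The strongest reply is that harm needs three things together: menarche before 13, unprotected sexual activity at that age, and failure to notice at visits held every four weeks. Exclusion 13 accepts total abstinence, where it is the patient's usual way of life, as effective contraception. A sexually inactive girl of 11 or 12 therefore already complies, whether or not her status has been re-checked. That stands, and it lowers the practical stake considerably.

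Other safeguards exist. The Week 48 serum test has no age limit, so the site must decide each girl's status at that visit, and SAP 5.5 (deviation G14) records a missed one. A serum test may be done whenever the investigator sees a need. There is a physical examination at every visit (7.2.2.1) and adverse-event questioning (8.1.1). These count, but only in part. The listed content of the examination includes no menstrual history or pubertal assessment, and a discretionary test presupposes suspicion.

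The background also points to small numbers and limited harm. Section 1.1 lists failure of sexual maturation among the complications of iron overload, and section 1.2.1.1 describes deferasirox as not teratogenic in animals. Both are fair limits. However, section 1.1 links the first to regular transfusion, and the trial also enrols non-transfusion-dependent patients.

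A reader might also infer from the row "Serum/ urine pregnancy test" in Table 7-2, marked only at Visit 15, that the age limit leaves girls untested throughout the extension. The documents do not support this. That schedule is the same for every female, including adults known to be fertile, and removing the age clause would add no scheduled test to it.

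**Conclusion.** The point holds as a minor safety gap. On either reading of the footnote, menarche before 13 prompts no scheduled re-check of childbearing potential before that age. How long the gap lasts depends on the reading: under the enrolment-age reading it is permanent for girls enrolled pre-menarche under 13, and under the current-age reading it ends at the first check after the thirteenth birthday, if she is still on study.

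The consequence is delayed recognition, not a lack of all protection. It would be wrong to conclude that girls under 13 have no safeguard, because the Week 48 test and the urine test after recognition both apply at any age. It would also be wrong to read this as a threat to the preference endpoint, the sample size or the analysis sets; none of them depends on it.

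The cut-offs rest only on the visit weeks and a 365.25-day year. The documents do not say how many girls enrol pre-menarche under 13 or how many reach menarche early on study, so the number affected is unknown. That it is small is a judgement.

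**What to change.** Delete the words *aged 13 and older* from Table 7-1 footnote 13 and Table 7-2 footnote 6. Every female who is pre-menarche at enrolment is then re-assessed at least every six months at an existing visit (for example Weeks 24, 48, 72 and 96), with the urine test at the next visit once she is able to bear children. This also removes the ambiguity about which age is meant.

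The cost is an amendment to two footnotes and one question at visits already planned. The question is uninformative in the youngest girls, and a few more urine tests would follow. No statistical section needs to change.
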